## 2. STUDY OBJECTIVES

### Primary objective:

- Confirm operational robustness and technical reliability of the software when operating in real-time in an operational ICU environment. We will measure indicators of system reliability and availability (e.g. what percentage of time is the system available, at different times of the day and night, on weekdays versus weekends, etc.) and the lag of the system (e.g. delay between data recorded at the bedside and model producing an output).

### Secondary objectives:

- In the shadow mode study, human evaluators will assess the AI decisions: off-duty clinicians will evaluate the clinical correctness/appropriateness of AI suggested decisions. The evaluators will classify the AI suggested actions in different categories, such as “likely safe”, “likely inappropriate”, “possible too low”, or “possibly too high”.
- We will document learning points and develop standard operating procedures for deploying the tool in various hospital systems
- Finally, we will estimate patients’ outcomes (organ failure, ICU mortality and hospital mortality) if the AI decisions were followed and compare them to actual outcomes (which were linked with human decisions).

## 3. STUDY DESIGN

This study is a prospective multi-centre observational study that will include four intensive care units from two different NHS Trusts.

The duration of the study will be up to 24 months.

We will include 100 to 300 adult patients with early sepsis in ICU (within 24h of ICU admission). This number is a pragmatic, realistic estimate of how many patients will satisfy the inclusion criteria in the study period (assuming a conservative 60 admissions per month on each unit (reality is closer to 80-100 pre-COVID-19), and 20% sepsis at admission), and will allow us to deliver on the study objectives.

With regards to human assessors, we will include 6 to 15 ICU doctors, mixing senior registrars, ICU fellows and consultants.

The “system” will be a purpose built webapp accessed from a dedicated laptop, connected to an NHS ICT server, with secure login. It will be linked to a duplicate of the Philips ICCA database (Imperial College Healthcare NHS Trust) or the EPIC EHR (UCLH) which contains ICU patient data in near real time (estimated lag of 5 to 15

minutes). The system will be running the AI Clinician algorithm, which processes ICU patient data and outputs a suggested dose of intravenous fluids and vasopressors. Four times a day (every 6 hours), the system analyses newly admitted ICU patients and identify those who fulfil the sepsis-3 criteria. If they do, they will be added to a list of patients for potential inclusion that will be accessible from within the software (and assessed by human evaluator for enrolment).

The system will contain several tabs:

- 1- **Patient screening.** It displays a list of patients screened and highlighted by the system as fulfilling sepsis-3 criteria. The user (human evaluator) has the option to include them into the study, after verification of the inclusion/exclusion criteria (see sections 4.2 and 4.3 for these criteria).
- 2- **Individual patient data.** This screen contains a drop-down list of patients included in the study. After selecting one, the data time series of this individual patient are displayed here, along with the doses of fluids and vasopressors actually given by human “on-duty” doctors and nurses.
- 3- **Evaluation tab.** This is where the evaluation of the AI and human doctors’ decisions takes place. The option to scroll through the various previous time points is provided. The evaluation by the human evaluator takes place in several subsequent steps: First, the human evaluator makes a recommendation based on patient data alone (data point #1). Then, the human evaluator is presented with the AI recommendation (data point #2), along with other information (confidence in the suggested decision, explanation of why this action was recommended). They “rate” the AI decisions, by classifying the AI suggested actions in different categories, such as “likely safe”, “likely inappropriate”, “possible too low”, or “possibly too high”. Finally, the human evaluator is presented with the actual decision (made by human clinicians, data point #3) and the subsequent patient evolution (at least a few hours, but the final outcome of ICU death or survival will be presented if available). The human evaluators rate the actual decisions using the same scale, e.g. “likely safe”, “likely inappropriate”, etc. There will be a free-text box to enable the user to provide feedback on their decisions.

The software will be accessed on the dedicated laptop from within the NHS hospitals by off-duty clinicians enrolled in the study, whom we call “human evaluators”. To explore system’s usability around the clock, there will be no restrictions with regards to timing of the research, so the human evaluators will be able to conduct the research at any time and on any day of the week.

We intend to conduct the study during 1-hour sessions, during which the users will conduct these 2 actions:

- 1) Identify new patients for inclusion from a pre-screened list
- 2) Assess multiple decisions made on multiple included patients. Based on a conservative number of 5 patients with sepsis on each unit at any point in time, and between 4 - 10 sessions per user, we will gather a maximum of 600 to 1,500 data points (100 data points per user for 6 to 15 users). We expect to include an estimated

100 to 300 separate patients across 4 sites (based on 20 patients per month per unit and 27 months of total study period over the 4 units, which gives 540 potential eligible patients). This will enable to complete the study objectives.

Data about the system's operational reliability will be automatically collected:

- Time elapsed between a clinical event (e.g., administration of a fluid bolus) and the record appearing in the database. This exploits the property of some clinical events to be time-stamped to quantify the lag in the system.
- Date and time of all system accesses
- Server status, down-time events, planned and unplanned outages. These events can be monitored remotely and logged by the ICT team.

An independent online form (survey-type) will be created to log all technical issues that the users may encounter (e.g., system unavailable, login issues etc). This survey will be kept separate from the system, so it can't be affected by server outage for example.

The data about the system's operational reliability and the technical issues reports do not contain patient sensitive information and will be available to researchers at Imperial College London, in the research groups of [name] and [name].

After running the study for 3 months on each study site, an interim analysis will be performed to test the data quality. A pseudo-anonymised dataset including the fields described in section 3.1 "study outcome measures" of all patients included so far in the study will be created. All patient identifiable information will be removed, patient NHS number will be replaced by an ad-hoc random number, and the mapping between the patients' true identity and identifiers will be kept on the NHS server. No patient health records will leave NHS systems.

The final analysis will occur at the end of the study period (after month 18, in August 2022), once all data has been collected. The pseudo-anonymised dataset will be transferred encrypted to an Imperial College London secured server, within the [name] Lab. Researchers in [name] and [name] groups will then conduct various modelling and analyses to assess the AI suggested decisions.

This trial will be conducted across four intensive care units: Imperial College Healthcare Trust - Charing Cross Hospital, Hammersmith Hospital, St Marys Hospital and University College London Hospital. All four units are capable of treating critically ill patients.

Routine clinical data (demographics, diagnosis, severity of illness, presence and duration of mechanical ventilation, ICU and hospital length of stay and hospital mortality, see appendix for more specific information) will be collected until hospital discharge from the recruiting centre. All outcome data will be collected from hospital databases including microbiology results.

To determine how the tool was implemented at each site, a trained researcher will accompany all site initiation visits to make observations and take field notes regarding discussions of planning and implementation at site.

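### The individual patient tab has no stated cut-off, so the protocol permits evaluators to see the dose under review and the later course before they give their own dose and rate the AI's

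*Protocol*

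**What the plan says.** Protocol section 3 (Study design) describes a web app used by off-duty ICU doctors, with separate tabs. In the individual patient tab the user picks an included patient from a list, and then "the data time series of this individual patient are displayed here, along with the doses of fluids and vasopressors actually given by human" clinicians on duty. No time limit is put on what is shown.

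The evaluation tab sets a sequence for each rated decision:

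- Step 1: "First, the human evaluator makes a recommendation based on patient data alone (data point #1".
- Step 2: the AI dose (#2) appears with its confidence and explanation, and the evaluator rates it.
- Step 3: "Finally, the human evaluator is presented with the actual decision (made by human clinicians, data point #3) and the subsequent patient evolution". The extent of that later course is given as "at least a few hours, but the final outcome of ICU death or survival will be presented if available". The evaluator then rates the actual dose.

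Of the same tab the protocol says: "The option to scroll through the various previous time points is provided". One of the two session tasks is "Assess multiple decisions made on multiple included patients", with "between 4 - 10 sessions per user". Section 3 also plans to log when the system is accessed.

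Sections 3.1 and 7 turn these entries into results: the evaluator's dose before and after the AI dose, #1–#2 and #2–#3 agreement, and the proportions of AI and actual decisions rated appropriate, too low or too high.

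**The concern.** The three-step order is the safeguard against anchoring and hindsight. It works only if the evaluator has not already seen the actual dose at that time point, or what happened afterwards. The protocol describes a second screen, open to the same person, that shows the doses given and is not tied to the time point being rated. It also fixes no order for rating several time points of one patient.

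If the dose under review is seen early, #1 may drift towards it. Agreement between #1 and #2 would then partly reflect agreement between the bedside team and the AI. If the later course is known, the rating of the AI dose may be coloured by how the patient fared. The first secondary objective is the evaluators' judgement of the AI's suggestions, and no analysis can restore independence that was lost when the rating was entered.

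**Working it through.** No arithmetic applies. The check compares what the evaluator should know at each step with what the described screens allow.

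| Moment | Evaluation tab (section 3) | Individual patient tab (section 3) |
|---|---|---|
| Before #1 is entered | Patient data only | Time series and doses given, no cut-off stated |
| Before the AI dose is rated | AI dose, confidence and explanation added | Same, no cut-off stated |
| After the AI rating | Actual dose and later course shown | Same |

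**Route 1: the individual patient tab**

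1. *Same user?* Section 3 says the software is used by the evaluators and states no limit by role on any tab.
2. *Are the withheld data already recorded?* Yes, on the natural reading. The evaluation tab scrolls back through earlier time points, and its last step must be able to show at least a few hours of later course. The rated decision therefore lies in the past.
3. *Is the display cut, masked or locked?* No section says so, and no order of opening the tabs is given.
4. *Result.* The text permits the dose under review and later data to be seen before #1 and before the AI rating. Doses given before the rated time point are legitimate patient data and are not part of the problem.

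**Route 2: the reveal itself**

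1. The last step for one time point shows later course and, where known, whether the patient survived the ICU.
2. Evaluators assess several decisions over several sessions. Nothing requires one patient's time points to be taken in chronological order, or reveals to wait.
3. *Result.* A reveal can disclose the dose or course at another time point of that patient, or the final outcome, before that other time point is rated. A cut-off on the individual patient tab would not cure this.

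**Which results depend on an unexposed evaluator**

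- Dependent: #1–#2 agreement, the dose before and after seeing the AI dose, and the AI rating proportions.
- Not dependent: the reliability and lag measures of the primary objective; #2–#3 agreement, which compares the algorithm's output with the recorded dose; the model-concordance comparison; and the off-policy evaluation. None of these uses an evaluator's dose or rating.
- The rating of #3 is made after the reveal by design, so early sight is not the issue there.

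**The case against.** The strongest reply is that this argues from silence. The individual patient tab gets a short summary, whereas the evaluation tab is named as the place where rating happens and states the intended masking plainly. How the software enforces it could sit in a software specification or in evaluator instructions. The results concerned are descriptive, serve a secondary objective and have no decision threshold. System accesses are already logged.

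Much of this is fair, and it limits the weight of the point. The intent to withhold is clear, and the software may already enforce it. But the stated order binds only the evaluation tab, and even there it does not govern several time points of one patient. A log of access times does not show which tab or time point was viewed before a rating, so exposed ratings might not be identifiable later.

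Three stronger readings are tempting and are not supported:

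- *That ratings will in fact be contaminated.* The protocol shows what is permitted, not what the built software displays or what evaluators will do.
- *That more than a day of course is always on screen at inclusion, because section 4.1 requires an ICU stay over 24 h.* Section 3 also speaks of early sepsis within 24 h of ICU admission and screens new admissions every 6 hours. The stay criterion may be confirmed later.
- *That repeat ratings of one patient can be counted.* Section 3 plans 100 data points per user over 4 to 10 sessions, so 100/10 = 10 to 100/4 = 25 per session. Dividing by "a conservative number of 5 patients with sepsis on each unit at any point in time" gives 2 to 5 per patient. If each decision yields three data points, it is 33.3/10/5 = 0.67 to 33.3/4/5 = 1.67. But 5 is the number present on a unit at one time, while the patient list holds everyone included, with 100 to 300 expected over the study. The denominator is doubtful, and neither figure counts exposed ratings.

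**Conclusion.** The point holds as a gap between two descriptions in section 3. As written, the protocol allows #1 and the AI rating to be made after sight of the dose under review or of later data, through the individual patient tab or through an earlier reveal for the same patient. Neither the share of ratings exposed nor the size of any bias can be derived from the document. The direction for #1–#2 agreement is also open, since it depends on how close the AI dose is to the dose given.

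The conclusion assumes that evaluators can open every tab, since no limit is stated, and that rated time points are past. The reach is confined to three descriptive evaluator results. The point should be settled, because the change is small and the information cannot be recovered afterwards, but it does not threaten the study's main purpose.

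**What to change.** Amend section 3 so that the two tab descriptions agree:

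1. While a time point is under evaluation, the individual patient tab and all time series are cut at that time, with earlier doses still visible, until #1 and the AI rating are saved with a timestamp.
2. When one evaluator rates several time points of one patient in a session, #1 and the AI rating are entered in chronological order, and the reveals follow once those ratings are saved.
3. Any #1 or AI rating made after a reveal for that patient in an earlier session is flagged and reported separately.
4. The access log already planned is extended to record tab and time-point views.

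Deferral should stay within the session. Carried across sessions it has no defined end, and because section 4.3 stops data collection when an evaluator withdraws, pending #3 ratings could be lost.

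The cost is some programming, less free browsing while a rating is open, a short delay of the #3 rating within the session, and fewer unexposed ratings in the flagged analysis. If the software already cuts the display, one sentence in the protocol settles item 1.

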## 7. STATISTICS AND DATA ANALYSIS

Data and all appropriate documentation will be stored for a minimum of 10 years after the completion of the study, including the follow-up period.

Data of interest	Statistical analyses
-------------------------	-----------------------------

System / usability data	Simple descriptive statistics (e.g. average system lag, number of technical issues per week...)
Anonymised patients' data	Simple descriptive statistics of the patient characteristics. Comparison of the training and prospective cohorts (simple parametric and non-parametric tests comparing demographics, severity of illness, etc).
Evaluators' data (the doctors assessing the AI in the background)	Descriptive statistics from evaluators data: Agreement between initial human evaluator doses (data point #1) and AI decisions (data point #2), and between AI decisions (data point #2) and actual doses given to patients (data point #3). Proportion of AI decisions (data point #2) classified as appropriate / possibly too low / possibly too high Proportion of human decisions (data point #3) classified as appropriate / possibly too low / possibly too high
AI decisions evaluation	Quantitative analyses of AI decisions: estimate patients' outcomes if the AI decisions were followed and compare them to actual outcomes (which were linked with human decisions). We will use 2 methods: 1) compare short-term outcomes between model-concordant treatment and model-non-concordant treatment, with confounder adjustment; 2) off-policy policy evaluation of the AI policy in the prospective ICHT cohort.

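### Evaluators rate the AI dose only after seeing its confidence and explanation, so the AI appropriateness proportion mixes dose quality with persuasion and is not like-for-like with the clinicians' proportion

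*Protocol*

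**What the plan says.** Protocol section 3 (Evaluation tab) fixes a sequence for each decision.

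- Own dose: "First, the human evaluator makes a recommendation based on patient data alone (data point #1").
- AI dose: "Then, the human evaluator is presented with the AI recommendation (data point #2"). The same screen adds supporting material before any rating is made: "along with other information (confidence in the suggested decision, explanation of why this action was recommended"). The evaluator then rates the dose.
- Actual dose: "Finally, the human evaluator is presented with the actual decision (made by human clinicians, data point #3) and the subsequent patient evolution"; in addition, "the final outcome of ICU death or survival will be presented if available". Only after this does the rating follow: "The human evaluators rate the actual decisions using the same scale".

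The protocol describes no rating of the AI dose before its confidence and explanation appear, no masking of source and no random order. It lists no rationale from the treating clinicians.

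Section 7 (evaluators' data) plans the proportion of AI decisions in each rating category and, as a parallel line, "Proportion of human decisions (data point #3) classified as appropriate / possibly too low / possibly too high". Both are descriptive.

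The second hypothesis in section 1.2 is that the AI suggestions are of appropriate quality as judged by off-duty clinicians. The first secondary objective in section 2 sets the target of the rating as clinical correctness or appropriateness. Section 3.1 also records the evaluator's recommended dose on either side of the AI dose being shown.

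**The concern.** A rating meant to describe the dose is taken when the evaluator has the dose, a statement of confidence in it and an argument for it. A favourable rating can then mean that the dose is sound, that the explanation was convincing, or both. An AI label could also lower ratings among evaluators who distrust the algorithm. The data as collected cannot separate these.

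Two results are at stake. The first is the AI proportion itself, on which the second hypothesis rests. The second is any reading of the two section 7 proportions against each other. They share a scale and categories, so readers will compare them, but one option comes with an argument and the other without, and only the second is rated with the later course in view.

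This cannot be left to the analysis stage. Display content and order are fixed at data collection, and a rating without the explanation that was never taken cannot be recovered.

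**Working it through.** **1. What each safeguard covers**

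| Element | Protects | Does not protect |
|---|---|---|
| Own dose recorded first (section 3, data point #1) | Agreement of evaluator dose with AI dose | Either rating |
| Agreement of AI dose with actual dose (section 7) | Uses no evaluator judgement | Either rating |
| Recommended dose before and after the AI dose (section 3.1) | Shows AI influence on the dose chosen | Either rating |
| Same scale for both ratings (section 3) | Common categories | Equal conditions of rating |

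The dose-agreement results are sound on this point. The rating proportions are not covered.

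**2. The plan's own figure**

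Section 3 expects at most 600 to 1,500 data points, at 100 per evaluator and 6 to 15 evaluators: 100 × 6 = 600 and 100 × 15 = 1,500. Both reproduce.

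**3. Possible size of the effect (assumptions throughout)**

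The protocol gives no expected proportion and no effect of explanation. Let q be the true appropriate share and f the share of otherwise unfavourable AI ratings that the display turns favourable. The inflation is f × (1 − q).

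| q | f = 0.1 | f = 0.2 | f = 0.3 |
|---|---|---|---|
| 0.70 | 3 points | 6 points | 9 points |
| 0.80 | 2 points | 4 points | 6 points |

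This illustrates an upward effect only; a downward effect is equally possible.

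**4. Sampling error if ratings were independent**

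Half-width = 1.96 × √(p(1 − p)/n).

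- p = 0.80: 1.96 × √(0.16/600) = 3.2 points; 1.96 × √(0.16/1,500) = 2.0 points.
- p = 0.70: 1.96 × √(0.21/600) = 3.7 points; 1.96 × √(0.21/1,500) = 2.3 points.

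**5. Sampling error with clustering by evaluator**

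Assume 100 ratings per evaluator and an intraclass correlation of 0.05. The design effect is 1 + (100 − 1) × 0.05 = 5.95, and √5.95 = 2.44.

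- p = 0.80: 3.20 × 2.44 = 7.8 points (n = 600); 2.02 × 2.44 = 4.9 points (n = 1,500).
- p = 0.70: 3.67 × 2.44 = about 9.0 points; 2.32 × 2.44 = 5.7 points.

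**6. Reading the two together**

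With independent ratings, the f = 0.2 and f = 0.3 effects exceed the half-width in every case, and the f = 0.1 effects do so only for q = 0.70 with n = 1,500. With clustering at 0.05, no effect in the table clearly exceeds it at n = 600. At n = 1,500 only the 6-point and 9-point effects do. Clustering by patient would widen the intervals further. In all cases a larger n narrows the interval around the wrong value.

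**The case against.** The strongest defence is that showing the explanation is part of the product. The research question in section 1.2 concerns how the system performs, and section 3.1 words the measure as whether the AI dose appears appropriate. That is fair: an explained rating is worth having. It does not settle the matter, because section 2 asks for clinical correctness, and section 1.1 places display to clinicians and acceptability in a later stage outside this application. Taking both ratings serves both aims.

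It is also true that the second hypothesis concerns AI suggestions alone and that section 7 states no test between the two proportions. A reader might infer that the plan rests on a formal AI-versus-clinician comparison; it does not. The harm is to interpretation, and to the AI proportion in its own right.

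Other stronger readings also lack support:

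- That the bias must exceed sampling error. This fails over part of the range once ratings cluster by evaluator.
- That evaluators are judging colleagues from their own units. The protocol says only that they are off-duty ICU doctors working from within the hospitals.
- That the clinicians' rationale is excluded. None is listed, but none is ruled out.
- That nothing planned bears on AI influence. The before-and-after dose does, though for the dose and not for the rating.

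One tempting remedy, showing the two doses side by side as unlabelled options, would do damage: the dose recorded after the AI suggestion could no longer be attributed to the AI.

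**Conclusion.** The point holds. The protocol fixes a display under which the AI appropriateness proportion cannot be read as a property of the dose alone, nor set beside the human proportion as like-for-like. Size and direction cannot be derived from the protocol. The 2 to 9 points shown rest on assumed base rates of 70% and 80% and an assumed conversion of 10% to 30%. Whether an effect of that order stands out from sampling error depends on the evaluator correlation, for which 0 and 0.05 were tried.

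The consequence is confined to a secondary objective and the second hypothesis. The primary objective, technical reliability, and the planned dose-agreement analyses are not affected. The change is still worth making before data collection, because it is cheap then and impossible afterwards.

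**What to change.** **1. Reorder the evaluation screen.** After data point #1:

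- Show the AI dose alone. Collect its rating and the section 3.1 dose recorded after the AI suggestion.
- Show confidence and explanation. Collect a second rating of the AI dose.
- Show the actual dose. Collect its rating before the later course and outcome are revealed.

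Use the first AI rating for clinical appropriateness and the second for the explained tool. State in section 7 which is which.

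**2. Analyse the ratings as pairs.** Cross-tabulate the first AI rating against the actual-dose rating per decision. Report the AI-versus-clinician contrast as a paired difference where the doses differ, with intervals that allow for clustering by evaluator and patient. Show decisions where the doses coincide as a check on the total display effect (label, explanation, order and, if it is still shown first, outcome). That check does not isolate the label, and a wish to be consistent may pull it towards no difference.

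**Cost.** One extra click per decision, a changed screen in a web application already being built for the study, and one table. Limits remain:

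- Source masking is not achieved, because the patient-data tab shows the doses given.
- The second AI rating may be anchored on the first.
- The actual dose is still rated after the AI explanation has been seen, so the contrast is improved but not fully balanced.
- The dose recorded after the AI suggestion would reflect the AI dose without its explanation, and section 3.1 should say so.

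### The clinicians' decision is rated after the later patient course is shown, the AI decision before it, yet both are reported as parallel proportions

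*Protocol*

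**What the plan says.** Protocol section 3 describes the Evaluation tab as serving both sets of decisions ("This is where the evaluation of the AI and human doctors") and fixes an order: "The evaluation by the human evaluator takes place in several subsequent steps".

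- **Step 1.** The evaluator gives their own dose from the patient data only (data point #1).
- **Step 2.** The AI dose is displayed (data point #2), "along with other information (confidence in the suggested decision, explanation of why this action was recommended". The evaluator rates it.
- **Step 3.** "Finally, the human evaluator is presented with the actual decision (made by human clinicians, data point #3) and the subsequent patient evolution". The extent of that later course is "at least a few hours, but the final outcome of ICU death or survival will be presented if available". The text then continues: "The human evaluators rate the actual decisions using the same scale".

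On when sessions take place, section 3 says "there will be no restrictions with regards to timing of the research".

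Section 7 lists, on consecutive lines, the proportion of AI decisions (#2) and the proportion of human decisions (#3) falling into the same three categories: appropriate, possibly too low, possibly too high. Section 3.1 lists the evaluators' agreement with the AI dose but no rating of the actual decision, so the timing of the latter is set only in section 3.

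**The concern.** Two proportions on one scale, printed one after the other, will be read against each other. Section 1.1 encourages this by saying that shadow mode allows actual and AI-recommended decisions to be compared. Such a reading requires both ratings to be made with the same knowledge of the patient, and here they are not. The evaluator judges the clinicians' dose having seen how the patient fared, and judges the AI dose without that knowledge. Hindsight can pull a rating down after a poor course or up after a good one.

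The amount of hindsight also varies between ratings. The final outcome appears only where it is already known, and with no restriction on session times this will differ from one rated decision to the next.

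At stake is the interpretation of one listed analysis. A gap between the proportions could reflect decision quality, hindsight or both, and the data as collected cannot separate them.

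**Working it through.** **Information on screen when each rating is made (protocol section 3)**

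| | AI decision (#2) | Clinicians' decision (#3) |
|---|---|---|
| Position in sequence | Second step | Third and last step |
| Patient data up to the decision | Yes | Yes |
| Confidence and explanation | Yes | None described |
| Later course, at least a few hours | Not listed | Yes |
| ICU death or survival | Not listed | Yes, where known |
| Scale | Common scale | Common scale |
| Report in section 7 | Proportion in three categories | Proportion in the same three categories |

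In the written sequence, later course is on screen for all #3 ratings and for no #2 rating. Nothing elsewhere in the protocol provides a #3 rating before the reveal, masks the source of a decision, varies the order, or warns against comparing the two figures.

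**How many ratings are affected**

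The protocol's own count is "we will gather a maximum of 600 to 1,500 data points (100 data points per user for 6 to 15 users". It reproduces: 100 × 6 = 600 and 100 × 15 = 1,500. The protocol does not say whether a data point is one rated decision or one of the three numbered items, so both readings are shown.

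- One data point is one rated decision: at most 600 to 1,500 outcome-informed #3 ratings.
- #1, #2 and #3 are counted separately: 600 / 3 = 200 to 1,500 / 3 = 500.

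Number of ratings whose net move into or out of the appropriate category shifts the human proportion by 1 percentage point:

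- First reading: 0.01 × 600 = 6 to 0.01 × 1,500 = 15.
- Second reading: 0.01 × 200 = 2 to 0.01 × 500 = 5.

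**Illustration of scale, on assumptions that are not in the protocol**

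Suppose AI and human decisions are equally appropriate, with true proportion p. A share b of decisions is followed by a poor course, and seeing it leads evaluators to downgrade a fraction h of the human decisions they would otherwise have called appropriate. The human proportion becomes p(1 − bh), so the spurious gap is p × b × h.

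- Low end: p = 0.70, b = 0.20, h = 0.10 gives 0.014, or 1.4 percentage points.
- High end: p = 0.90, b = 0.40, h = 0.30 gives 0.108, or 10.8 percentage points.

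This only shows that plausible-looking inputs span a wide range. If good courses raise ratings, the gap runs the other way. It does not shrink as ratings accumulate, because it is bias and not sampling error.

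**The case against.** The strongest reply is that the protocol plans no contrast between the two proportions. Section 7 calls the evaluator analyses descriptive and states no difference, test or margin. The hypothesis in section 1.2 and the secondary objective in section 2 concern only whether AI suggestions are appropriate. This stands, and it limits the point. It does not remove it, because the human proportion is a listed analysis and is reported in the same form as the AI one.

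Second, the contrast may be less clean than the sequence suggests. That the rating follows the reveal is read from the order of the sentences. The Individual patient data tab shows the time series and the doses given, and nothing says later data are hidden when the AI dose is rated. This also stands in part: actual exposure at step 2 could exceed none. It would blur the designed asymmetry without making the two ratings equivalent.

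Third, the evaluator's own dose is recorded before the outcome step, so agreement of #1 with #2 and of #1 with #3 can be compared free of the step 3 display. That is useful, but it measures closeness of dose, not judged appropriateness. It does not replace a rating that was never taken.

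Fourth, hindsight review of the treatment given may be intended, since an observed course exists only for that treatment. The protocol gives no such reason, and a labelled rating after the reveal would preserve that purpose.

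**Conclusion.** The point holds. As written, every rating of a clinicians' decision is made with later course on screen and no rating of an AI decision is, and section 7 presents the two results in matching form. The difference between them therefore cannot be interpreted as a difference in decision quality. The magnitude and direction of the distortion are not derivable from the protocol.

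The conclusion rests on taking the First, Then, Finally order in section 3 as the order of display and rating; no other order is given. The scope is narrow: a secondary, descriptive item. The AI proportion in the written sequence, the planned dose agreement between #2 and #3, and the primary reliability objective are unaffected. It still merits correction because the defect lies in data capture. No analysis plan, including any SAP not seen here, can restore a pre-outcome rating afterwards.

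**What to change.** Split step 3 of the Evaluation tab in section 3. Show the actual dose alone, record and lock its rating, and only then reveal the later course and outcome. For the lock to work, the later course should not be reachable through the Individual patient data tab before the rating is stored. If a judgement made with hindsight is wanted, keep it as a separate item labelled outcome-informed.

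If the present order is kept, or for ratings already collected under it, label the human proportion in section 7 as outcome-informed and state that it is not to be compared with the AI proportion.

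Neither route makes the ratings fully equal. The AI dose is still rated first and comes with confidence and an explanation, while none is described for the actual dose. State this as a limitation beside the two proportions.

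The cost is small. The webapp is purpose-built and already runs stepwise, so one existing step becomes two, with no extra patients or evaluators. The optional rating after the reveal adds one entry per decision. The labelling alternative is one line in section 7.
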